Appendix

[figure not shown]
- A Sample Informed Consent Form
- B Declaration of Helsinki
- C GSRS-HRQL Quality of Life Assessment
- D GERD-HRQL Quality of Life Assessment
- E Reflux Disease Questionnaire
- F Reflux Symptom Index

1. Introduction and History of Prior Investigations

The need for a safe, effective, and durable treatment of gastroesophageal reflux disease (GERD) has become increasingly apparent in the past 15 years as a result of a growing prevalence and incidence of this chronic disease.¹⁻⁶ The likelihood of developing GERD increases with the severity of anatomical change and dysfunction of the gastroesophageal (GE) junction, which represents the primary defense against reflux of gastric content into the esophagus.^{7-12, 13} Restoration of the gastroesophageal junction competence at the anatomic, mechanic and physiologic levels is critical for an effective long-term treatment of GERD.² At the same time, complications and new onset symptoms associated with traditional laparoscopic Nissen fundoplication, including dysphagia and gas bloat must be avoided.

A novel transoral incisionless device was developed in an attempt to mimic well established and long term proven principles of antireflux surgery via constructing a fundoplication at the gastroesophageal junction, restoring the angle of His, increasing sphincter augmentation, recreating the high pressure zone and reducing small hiatal hernia, but with fewer side effects. The EsophyX™ system with SerosaFuse fasteners (EndoGastric Solutions, Redmond, WA, USA) has been cleared by the U.S. FDA for treatment of GERD and reduction of ≤ 2 cm hiatal hernia and has been successfully used to reconstruct the gastroesophageal junction through partial fundoplication with tailored delivery of multiple fasteners during a single-device insertion (**Figures 1,2,3**).¹⁴

The technique has been refined resulting in a significantly higher normalization rate of esophageal acid exposure and a significant increase of LES pressure and length, combined with long term symptom control.

The Esophyx device has been well-established for the indication of GERD treatment by the U.S. FDA through numerous Class II device 510(k) pre-market clearances dating back to 2009 (and most recently K160960). A summary of past clinical trials has been provided in Table 2. Based on the success of prior TIF surgeries, EndoGastric Solutions has recently fine-tuned the Esophyx device allowing for more user-friendly and automatic, stapler-like reliable fastener deployment, as stylet manipulation is no longer required (See “3. Device Description” section). Neither the initial Intended Use nor the Indications for Use have been altered as a result of this design refinement. The FDA cleared Indications for Use is provided below.

“The EndoGastric Solutions EsophyX Z System with SerosaFuse Fastener and Accessories is indicated for use in transoral tissue approximation, full thickness plication and ligation in the GI tract and is indicated for the treatment of symptomatic chronic gastroesophageal reflux disease in patients who require and respond to pharmacological therapy. It is also indicated to narrow the gastroesophageal junction and reduce hiatal hernia ≤ 2cm in size in patients with symptomatic chronic gastroesophageal reflux disease.”

The current $\leq 2\text{cm}$ hiatal hernia size limitation presents a problem for treating patients with hiatal hernias $>2\text{ cm}$. Traditionally, these patients, with more advanced anatomical defects, have been surgically treated via a laparoscopic Nissen Fundoplication (NF). Although laparoscopic, the NF is a complex and relatively invasive procedure best performed by very experienced surgeons in order to increase the probability of achieving the desired repair of the hiatal hernia and completion of a total circumferential 360 degree “floppy” wrap without the complications of dysphagia and gas bloat.

A recent $n=64$, 10-year follow-up study showed a 10.9% defective fundic wrap in laparoscopic Nissen candidates.¹ Due to the fundamentally different approaches between TIF and Nissen procedures, the serious risks associated with Nissen that are inherently absent from the EsophyX TIF 2.0 technique include: excessive scarring, vagus nerve injury, dysphagia, gas bloat, and vomiting/ eructation inhibition from supra-physiological fundic overwrapping.²

Historically, clinical results, with patients presenting with $\leq 2\text{cm}$ hiatal hernias, have demonstrated that the TIF procedures using the EsophyX system with SerosaFuse fasteners is effective in eliminating symptoms, decreasing the need for daily PPIs, normalizing esophageal acid exposure, increasing LES resting pressure, and promoting healing of esophagitis in more than 80% of patients with chronic GERD. The obtained improvement in clinical and pathophysiological outcomes correlated significantly with the quality of the anatomic reconstruction. This clinical study is designed to explore use of the TIF procedure in patients who have had their hiatal hernias reduced from between $>2\text{cm}$ and $\leq 4\text{ cm}$ to $\leq 2\text{cm}$. Demonstration that TIF results with these patients are similar to TIF results from patients initially presenting with $\leq 2\text{cm}$ hiatal hernias while avoiding traditional NF complications could provide expanded patient choices in the minimally invasive treatment of GERD.

¹ Neuvonen, Perttu, Mauri Iivonen, and Tuomo Rantanen. "Endoscopic evaluation of laparoscopic nissen fundoplication: 89% success rate 10 years after surgery." *World journal of surgery* 38.4 (2014): 882-889.

[figure not shown]
² Waring JP (1999). "Postfundoplication complications. Prevention and management". *Gastroenterol. Clin. North Am.* 28 (4): 1007–19, viii–ix. doi:10.1016/S0889-8553(05)70102-3. PMID 10695014.

	RESPECT¹⁶	TEMPO^{17,18,19}	TIF vs. Sham²⁰	TIF Registry^{21,22,23}	STAR Registry
Design	A multi-center, randomized, single-blind, controlled TIF/Placebo vs. Sham/PPIs trial	A multi-center, randomized, open-label, controlled TIF vs. PPI trial	A multi-center, double-blind, sham controlled randomized trial	A multi-center, prospective, open-label, post market registry	An AGA-sponsored, multi-center, prospective, open-label, post market registry
Objective	To compare safety and effectiveness of TIF vs. Sham/PPIs in patients with “troublesome symptoms” specifically regurgitation	To compare safety and efficacy of TIF vs. PPIs for the treatment of chronic medically refractory GERD	To gauge the time to ‘treatment failure’ during the first 6 months after intervention	To evaluate the safety and efficacy of TIF in a broad range of GERD patients treated in routine clinical practice	To compare the safety and efficacy of TIF procedure vs. Laparoscopic Nissen Fundoplication Surgery (LNF)
Patients	2:1 ratio TIF/Placebo group (n=80) vs. Sham/PPI group (n=40)	2:1 ratio TIF group (n=28) vs. PPIs group (n=14)	1:1 ratio TIF group (n=22) vs. sham group (n=22)	274 patients treated with TIF procedure	1:1 ratio TIF group (n=250) vs. LNF group (n=250)
Duration(s)	6 months, 1 year w/ crossover (abstract)	6 months, 1 year w/ crossover, 3 years	6 months	6 months, 1 year, 2 years	Ongoing
Key Outcomes	
 ✓ Troublesome regurgitation was eliminated in 72% of TIF patients at > 1Y ✓ Median heartburn score decreased from 17 to 5 at 6 months and to 3, at > 1Y post-TIF ✓ Complete cessation of PPI therapy was achieved in 72% of TIF patients > 1Y 	
 ✓ All symptomatic outcome measures were stable between 1Y, 2Y and 3Y follow-up ✓ Esophagitis was healed in 86% of patients at 3Y follow-up ✓ 71% of patients completely off PPIs at 3Y follow-up ✓ Improvement in pH parameters remained stable at 3Y follow-up 	
 ✓ Average of 197 days “time in remission” post-TIF vs. 107 days post-sham ✓ Six months post-op 13/22 (59%) of TIF patients were in clinical remission with complete cessation of PPIs consumption. ✓ 69% of the TIF group normalized esophageal acid exposure vs. 20% of the sham group 	At 2Y follow-up: 
 ✓ 65% normalization in the Reflux Symptom Index score ✓ 74% normalization of Gastroesophageal Reflux Symptom Score ✓ A decrease from 91% to 29% in daily PPI use ✓ 75% of patients had esophagitis healed 	In enrollment

Table 2. Summary of Level I and II Clinical Studies (TIF 2.0)

2. Device Description

The EsophyX® Z device is a single use, hand-held flexible instrument that is introduced transorally with a flexible endoscope in the center of the device, so the entire procedure can be done safely under direct visualization. The device is designed so the physician can manipulate esophageal and gastric tissue, creating a partial fundoplication, secured by and deploy strong, H-shaped fasteners in order to reconfigure lower esophageal anatomy to prevent GERD.

3. Study Design Rationale

In spite of the promising results described in the previous section, the TIF 2.0 procedure with EsophyX Z is not an ideal option for all GERD patients. Early GERD syndrome and disease is clearly best medically treated with antacids, H2 blockers and/or Proton Pump Inhibitors (PPIs). These pharmacological approaches may be palliative but are both highly effective and believed to be very safe at labeled dosages and durations, in early stage of the disease. The current general Gastroenterology consensus, as documented in the American Gastroenterological Association (AGA) Medical Position Statement on “The Management of Gastroesophageal Reflux Disease”, is that only patients who are either intolerant of PPIs, or who have persistent troublesome symptoms while on properly adjusted doses of PPIs should be considered for antireflux surgery. “Troublesome” symptoms in this context are defined by

the “Montreal Consensus”¹ as mild symptoms occurring two (2) or more days per week, or moderate/severe symptoms occurring more than 1 day per week.

Frequently, patients exhibiting GERD symptoms and Hiatal Hernias are treated with Nissen fundoplications. However, the Nissen technique is complex, and requires significant training and expertise to perform. Many surgeons lack the requisite experience and resources to perform such a procedure safely and effectively. Demonstration of TIF effectiveness post hiatal hernia reduction from up to 4 cm, gastroenterologists would have an option as opposed to referring patients to select hospitals for a Nissen.

As in RESPECT RCT, patients are required to cease PPI intake 7 days prior to the procedure to ensure of accurate pH measurement via the BRAVO capsule.

In this context, an ideal study would consist of enrolling patients who suffered from persistent troublesome symptoms while on optimized dose of PPIs. The prospective study is open-label, non-randomized, and investigator initiated at multiple (3) sites (n=50). The primary endpoint is a clinically significant pH improvement, i.e. normalization, at the 6 month post-op mark. The proportion of patients with normalized esophageal acid exposure after 6 months will be compared to that of the previous EsophyX RESPECT trial to demonstrate equivalent (non-inferior) effectiveness. A sequence of follow-up visits will be required (2 week, 3 month, 6 month) to monitor symptom presence and PPI intake via Quality of Life surveys in addition to the primary endpoint. This follow-up and symptom monitoring will include evaluation of potentially new onset symptoms such as dysphagia and gas bloating commonly associated with the NF procedure.

4. Study Objective

Evaluation of the relative merits, safety and effectiveness of the EsophyX Z transoral device in performing an advanced TIF procedure preceded by laparoscopic Hiatal Hernia repair (hiatal hernias >2cm and \leq 4 cm) in PPI- prescribed patients with “troublesome symptoms” per the Montreal consensus definition.

5. Study Hypotheses

5.1. *Primary Efficacy Hypothesis 1*

At 6-month follow-up, the proportion of TIF patients with normalized esophageal acid exposure will be statistically non-inferior to results from the EGS RESPECT study.

5.2. *Secondary Efficacy Hypothesis 1*

The proportion of TIF2 patients who are free of “troublesome” symptoms will be the same as or higher than the results from the EGS RESPECT study.

5.3. *Secondary Efficacy Hypothesis 2*

At 6-month follow-up, \geq 50% of the TIF patients will have a clinically significant reduction in PPI consumption as compared with their pre-TIF consumption

5.4. *Primary Safety Hypothesis 1*

At 6-month follow-up, no increase in medically significant adverse events as compared with the RESPECT study

5.5. *Secondary Safety Hypotheses 1*

[figure not shown]
At 6-month follow-up, no new onset symptoms and side effects frequently associated with Nissen fundoplication procedures including dysphagia and gas bloat.

6. Study Design**6.1. *Study Population***

The study population will consist of patients with chronic “troublesome” GERD symptoms while on PPIs and proven anatomic deterioration of the gastroesophageal junction who prefer a laparoscopic Hiatal Hernia Repair followed by an endoscopic intervention (TIF 2.0) over the long term treatment of PPIs. These patients should have well documented GERD with or without endoscopic signs of esophagitis, hiatal hernia >2cm and up to 4 cm and a history of > 6 months of daily use of PPI to control major GERD symptoms.

6.2. *Study Schematic Design*

Please see next page.

**Figure 6. Schematic of Study Design**

7. Study Population

7.1. Selection Criteria

The table on the following pages outlines the specific inclusion and exclusion criteria for the study. Before randomization in the study, a patient must meet all of the inclusion and exclusion criteria.

Inclusion Criteria:	
1.	Age 18-80years
2.	Dependent upon daily PPIs for > 6 months. Daily use is defined as a double dose, or full dose or half dose taken daily for more than 80 % of the total number of days during the proceeding evaluation period
3.	Troublesome symptoms, specifically heartburn or regurgitation, while on optimized dose of PPI's. Troublesome heartburn or regurgitation symptoms are those which occur a minimum of 2 days a week and are mild to severe in severity.
4.	Abnormal ambulatory (Bravo) pH study after off PPI therapy for 7 days, i.e. >5.3% of the time with pH < 4 in a 48-hour monitoring period
5.	Normal or near normal esophageal motility (by Upper GI/ esophagram or manometry as required)
6.	Pre-enrollment Hiatal Hernia (axial height and transverse dimension) from > 2cm and up to 4 cm inclusive
7.	Patient willing to cooperate with post-procedure dietary recommendations and assessment tests at the requisite follow-up visits
8.	Signed informed consent
Pre-enrollment Exclusion Criteria:	
1.	BMI > 35
2.	Hiatal hernia \leq 2 and > 4 cm
3.	Esophagitis Los Angeles grade C or D
4.	Esophageal ulcer
5.	Esophageal stricture
6.	Long-segment Barretts esophagus (Prague: C > 1, M > 3)
7.	Esophageal motility disorder
8.	Pregnancy or plans for pregnancy in the next 12 months (in females)
9.	Immunosuppression
10.	ASA > 2
11.	Portal hypertension and/or varices
12.	History of previous resective gastric or esophageal surgery, cervical spine fusion, Zenker's diverticulum, esophageal epiphrenic diverticulum, achalasia, scleroderma or dermatomyositis, eosinophilic esophagitis, or cirrhosis
13.	Active gastro-duodenal ulcer disease
14.	Gastric outlet obstruction or stenosis
15.	Severe gastroparesis or delayed gastric emptying confirmed by solid-phase gastric emptying study if patient complains of postprandial satiety during assessment
16.	Coagulation disorders
17.	Symptoms including gas bloat and dysphagia.
18.	Any other presenting condition that in the opinion of the investigator would not make participation in this study in the patients best interest.
Post-enrollment Exclusion Criteria:	
1.	Inability to repair Hiatal hernia with at least 2cm of intra-abdominal esophagus length.

7.2. *Withdrawal*

While study withdrawal is discouraged, patients may withdraw from the study at any time, with or without reason and without prejudice to further treatment. Withdrawn patients will not undergo any additional follow-up. In all cases of withdrawal, the reason(s) for withdrawal (if given) will be recorded upon study termination.

8. Study Methods and Techniques

8.1. *Clinical Symptom Assessments*

The following four GERD-specific questionnaires will be used to assess typical and atypical symptoms, their frequency and intensity, as well as their impact on daily life, relationships, quality of life, state of mind, worries and concerns, sleep and diet.

- Reflux Disease Questionnaire (RDQ)
- GERD HRQL Quality of life assessment
- GERD GSRS Quality of life assessment
- RSI Questionnaire for atypical symptoms

- The time needed for completion of all four questionnaires is estimated for 35 minutes maximum.
- A $\geq 50\%$ improvement in the total GERD-HRQL and GERD-GSRS scores compared to the baseline off PPIs will be considered clinically significant.
- A reduction in severity from \geq moderate to \leq mild and/or a reduction in frequency from ≥ 2 days per week to ≤ 1 day per week is indicative of a clinically significant result as measured by the Reflux Disease Questionnaire (RDQ).

8.2. *PPI Usage*

The use of PPIs plus other GERD medication such as histamine receptor antagonists (H2RA) and antacids will be recorded in a medication diary using generic names (**Table 3**) and classified according to the daily dose and frequency.^{18, 21}

Usage will be defined as “Daily” if a double dose, full dose or half dose is taken daily for more than 80% of the total number of days during the proceeding follow-up period.

Note: “Full Dose” is defined as the first number of mg listed for each PPI in the following table.

Table 3. Proton Pump Inhibitors (PPI)

Generic Name	Brand Names	Available Pill Sizes (mg)
Esomeprazole	Nexium	20, 40
Lansomeprazole	Prevacid, Dakar, Lando, Lanzor, Prezal, Lanzol	15, 30
Omeprazole	Prilosec, Losec, Logastric	10, 20, 40
Pantoprazole	Protonix, Zurcal, Pantozol, Zurcale	20, 40
Rabeprazole	Aciphex, Pariet	20

8.3. *Upper GI Endoscopy*

- Diagnosis of esophagitis according to the Los Angeles classification confirmed by esophageal biopsy.²²
- Hiatal hernia size will be diagnosed based on the distance from Z-line to diaphragmatic impression measured in cm at retraction of the endoscope without insufflation.
- Geometrical aspects of the TIF valves will be assessed by evaluating their:
 - Length**, defined as the length in cm from the apex of the fundus to the valve lip as demonstrated in **Figure 7**;²³
 - Circumference**, defined as the distance in degrees between the two most distant fasteners as demonstrated in **Figure 4**;
 - Adherence** to the endoscope defined as tight, moderate or loose;
 - Grade using **Hill classification** system,²⁴ defining grade I by the presence of a prominent tissue fold surrounding the endoscopic shaft; grade II by the presence of a moderately prominent tissue fold which rarely opens with respiration and closes promptly; grade III by a barely present fold which fails to close around the endoscope; and grade IV by the lack of a muscular fold with lumen of esophagus staying open all the time allowing the squamous epithelium to be viewed from below.

[figure not shown]

Figure 7. Schematic drawing of TIF valve and its geometric aspects (Illustration from Cadiere et al 2008¹⁶)

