Pre-enrollment Exclusion Criteria	
 1. BMI > 35 2. Hiatal hernia \leq 2 and > 4 cm 3. Esophagitis Los Angeles grade C or D 4. Esophageal ulcer 5. Esophageal stricture 6. Long-segment Barretts esophagus (Prague: C > 1, M > 3) 7. Esophageal motility disorder 8. Pregnancy or plans for pregnancy in the next 12 months (in females) 9. Immunosuppression 10. ASA > 2 11. Portal hypertension and/or varices 12. History of previous resective gastric or esophageal surgery, cervical spine fusion, Zenker's diverticulum, esophageal epiphrenic diverticulum, achalasia, scleroderma or dermatomyositis, eosinophilic esophagitis, or cirrhosis 13. Active gastro-duodenal ulcer disease 14. Gastric outlet obstruction or stenosis 15. Severe gastroparesis or delayed gastric emptying confirmed by solid-phase gastric emptying study if patient complains of postprandial satiety during assessment 16. Coagulation disorders 17. Atypical symptoms including gas bloat and dysphagia. 18. Any other presenting condition that in the opinion of the investigator would not make participation in this study in the patient's best interest.

Post Enrollment Exclusion	1. Inability to repair Hiatal hernia with at least 2cm of intra-abdominal esophagus length.
Intervention	
Treatment: Standardized Transoral Incisionless Fundoplication (TIF 2.0) using EsophyX ZR system with SerosaFuse fasteners (EndoGastric Solutions, Inc., Redmond, WA, USA) preceded by Hiatal Hernia repair.
 
Control: Each patient will serve as his/her own control (condition prior to HH repair and TIF 2.0)

Evaluation Criteria	
Primary Effectiveness Endpoint: Normalization in esophageal acid exposure is defined by $\leq 5.3\%$ of total time pH < 4 in a 48-hour monitoring period.
 
Secondary Effectiveness Endpoint 1: Per Montreal Consensus definition, troublesome symptoms are mild symptoms occurring two (2) or more days per week, or moderate/severe symptoms occurring more than 1 day per week.
 
Secondary Effectiveness Endpoint 2: Clinically significant PPI consumption reduction is defined as from daily use to occasional use or none at all. Daily use is defined as a double dose, or full dose or half dose taken daily for more than 80 % of the total number of days during the proceeding evaluation period.

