10.2.2 Effectiveness Analysis

The primary analysis timepoint for effectiveness is 6 months post TIF procedure. Descriptive summaries as described in 10.2.1 General Methodology will be provided for the primary effectiveness endpoint of proportion of patients with normalized esophageal acid exposure, and secondary endpoints of proportion of patients free of “troublesome” symptoms and proportion of patients with a clinically significant reduction in PPI consumption from their pre-TIF screening consumption.

At each assessment time point, RDQ, atypical symptom RSI, Quality of Life questionnaires GSRS, HRQL will summarized as continuous measures. At 6 months, changes from baseline will be similarly summarized for each of these instruments. As defined in Section 8.1, portions of patients with clinically significant improvements will also be reported with 95% confidence intervals for GERD-HRQL, GERD-GSRS, RSI, and RDQ.

In addition, for the primary endpoint, proportion of patients with normalized esophageal acid exposure, 44% was observed in the EGS RESPECT study. Non-inferiority testing will be conducted for the same proportion observed in the HEURISTIC study vs. the RESPECT result. The hypotheses are as follows.

H_0 : HEURISTIC 6-month normalization rate $\leq 44\% - 20\% = 24\%$

H_A : HEURISTIC 6-month normalization rate $> 44\% - 20\% = 24\%$

The HEURISTIC normalization rate will be considered non-inferior to the 44% RESPECT rate if H_0 can be rejected at a 1-sided $p < 0.05$ level by exact binomial

probability calculation. To achieve this goal in 50 evaluable patients, the observed 6-month normalization rate in HEURISTIC must be 18/50 (36%) or higher.

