10.2.3 Safety Analysis

Treatment emergent adverse events, i.e. adverse events occurring during or after the first protocol procedure (i.e. hiatal hernia reduction), will be summarized. The proportion of patients with medically significant adverse events will be compared to the same proportions observed in the RESPECT study.

In addition, the number and proportion of subjects reporting any given adverse event, including any clinically significant hiatal hernia repair complications and new onset symptoms (dysphagia, gas bloat) should they occur, will be tabulated. Separate tables will be constructed for (a) all reported treatment emergent adverse events, (b) protocol procedures (hiatal hernia reduction, TIF) related adverse events, and (c) serious adverse events.

10.1. *Sample Size and Power Estimation*

For the primary endpoint, proportion of patients with normalized esophageal acid exposure at 6 months post TIF procedure, 44% was observed in the EGS RESPECT study. It is assumed that the true underlying rate for HEURISTIC treatment would be the same, i.e. 44%. In order to reject an inferior normalization rate of 24% at a 1-sided $p < 0.05$ level, the observed 6-month normalization rate in HEURISTIC must be 18/50 (36%) or higher. With 50 evaluable subjects, the chance (power) for successfully reaching this goal is 0.90.

11. Clinical Effectiveness Endpoints and Evaluation Criteria

11.1. *Clinical effectiveness*

Primary effectiveness endpoint and evaluation criterion

The primary efficacy endpoint is normalization in esophageal acid exposure at 6 months post TIF procedure. Normalization in esophageal acid exposure is defined as $\leq 5.3\%$ of time with $\text{pH} < 4$ in a 48-hour monitoring period.

Secondary effectiveness measures and evaluation criteria

Secondary effectiveness measures include free of “troublesome” heartburn and/or regurgitation symptoms and a clinically significant reduction in PPI use.

Per Montreal Consensus definition, troublesome symptoms are mild to severe symptoms which occur a minimum of 2 days a week.

A clinically significant PPI consumption reduction is defined as from daily use to occasional use or none at all. Daily use is defined as a double dose, or full dose or half dose taken daily for more than 80 % of the total number of days during the proceeding follow-up period.

Table 5. Study Effectiveness Endpoints and Success Criteria

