Study Endpoints/Outcomes	Control	Pre-procedure Value	Post-procedure Value	Success Criteria
PRIMARY EFFECTIVENESS				
Normalized acid exposure	Self-Comparison	BRAVO Ph studies after off anti-secretory meds ≥ 7 days	BRAVO Ph studies at 6 months after off anti-secretory meds ≥ 7 days	Treatment success will be defined by a proportion of TIF patients with normalized acid exposure that is non-inferior to the RESPECT result as defined in 10.2.2.
SECONDARY EFFECTIVENESS				
GERD symptoms	Self-Comparison	Reflux Disease Questionnaire (RDQ) scores	Reflux Disease Questionnaire (RDQ) scores at and 6 months	Treatment success will be defined by a proportion of TIF patients free of troublesome symptoms at 6 months that is \geq the same proportion in RESPECT Trial (67%)
PPI usage	Self-Comparison	PPI usage (must be "daily")	PPI usage at 6 months	Treatment success will be defined by $\geq 50\%$ of TIF patients that has a clinically significant reduction, i.e. from "daily" PPI use to "none" or "occasional" use, at 6 months.

12. Risks

The following risks are anticipated and can result from the TIF procedure or general anesthesia:

Expected typical risks or discomfort:

- Pharyngolaryngeal pain (e.g., sore throat)
- Musculoskeletal pain (e.g., left shoulder pain)
- Temporary epigastric or abdominal pain, which can be treated with standard pain medication
- Temporary dysphagia (i.e., difficulty swallowing) due to swelling
- Nausea or vomiting

Unusual risks or discomfort:

- Oral or dental injury
- Bleeding
- Bloating sensation
- Hematoma

Rare risks:

- Esophageal perforation, laceration or tear
- Aspiration, hypoxia, achalasia

- Nerve damage
- Arrhythmia
- Pneumothorax, chest pain
- Pneumoabdomen
- Fistula
- Infection of the mediastinal space

Additional risks:

- Operation to remove a defective device or its parts
- Reoperation after a failed procedure (insufficient symptom relief)

13. Adverse Events

All adverse events will be monitored from the time of enrolling through the 6-month follow-up visit. Unanticipated adverse device effects (UADE) and SAEs will be monitored through the 12-month follow-up.

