11. Does regurgitation change your diet?	 0  1  2  3  4  5
12. Does regurgitation wake you from sleep?	 0  1  2  3  4  5
13. Do you have difficulty swallowing?	 0  1  2  3  4  5
14. Do you have pain with swallowing?	 0  1  2  3  4  5
15. If you take medication, does this affect your daily life?	 0  1  2  3  4  5
16. How satisfied are you with your present condition?	 0  1  2  3  4  5

Satisfied Neutral Dissatisfied

Appendix E – Reflux Disease Questionnaire**Reflux Disease Questionnaire**Please answer each question by ticking one box per row.**1. Thinking about your symptoms over the last seven days, how often did you have the following?**

	Did not have	Less than one day a week	One day a week	2-3 days a week	4-6 days a week	Daily
a. A burning feeling behind your breastbone						
b. Pain behind your breastbone						
c. A burning feeling in the centre of the upper stomach						
d. A pain in the centre of the upper stomach						
e. An acid taste in your mouth						
f. Unpleasant movement of material upwards from the stomach						

2. Thinking about symptoms over the last seven days, how would you rate the following?

	Did not have	Very mild	Mild	Moderate	Moderately severe	Severe
a. A burning feeling behind your breastbone						
b. Pain behind your breastbone						
c. A burning feeling in the centre of the upper stomach						
d. A pain in the centre of the upper stomach						

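### The Section 8.1 RDQ responder rule can count a patient as clinically improved when severity or frequency has worsened

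*Combined protocol and SAP*

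**What the plan says.** Section 8.1 joins the two limbs of the RDQ rule permissively: "mild and/or a reduction in frequency from" is the connecting text, so a qualifying fall in severity or a qualifying fall in frequency is enough. A patient who meets either limb has a result that "is indicative of a clinically significant result as measured by the Reflux Disease Questionnaire (RDQ". The section sets no condition on the dimension that did not qualify.

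Section 10.2.2 points back to Section 8.1 and states that "portions of patients with clinically significant improvements will also be reported with 95% confidence intervals for GERD-HRQL, GERD-GSRS, RSI, and RDQ". No hypothesis test is attached to these proportions.

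Section 11.1 defines a separate status: "troublesome symptoms are mild to severe symptoms which occur a minimum of 2 days a week". The synopsis words it slightly differently: "troublesome symptoms are mild symptoms occurring two (2) or more days per week, or moderate/severe symptoms occurring more than 1 day per week". Table 5 bases the symptom endpoint on that status and not on the Section 8.1 rule: "Treatment success will be defined by a proportion of TIF patients free of troublesome symptoms at 6 months", judged against 67% in RESPECT.

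The form in Appendix E scores frequency and severity separately, item by item. Each has six levels. Severity runs from not present through very mild, mild, moderate and "Moderately severe" to severe. Frequency runs from not present through less than one day, one day, 2-3 days and 4-6 days a week to daily.

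**The concern.** A measure labelled clinically significant improvement should not admit a patient whose symptoms have become more severe, or more frequent, than at baseline. The Section 8.1 rule looks at one dimension at a time and ignores what happened to the other, so it can do exactly that.

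What is at stake is the meaning of one reported proportion. The study is single-arm and open-label, so there is no concurrent group, scored by the same rule, against which a lenient definition would cancel out. A reader of the report would take the RDQ responder rate as the share of patients who got better, and could not tell from it how many had traded one dimension against the other.

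**Working it through.** The documents state no figure for the RDQ responder rate, so there is nothing to reproduce. The check is a listing of every change that a single RDQ item can record.

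**Inputs**
- Responder rule: Section 8.1, either limb.
- Troublesome: Section 11.1, mild or worse on two or more days a week. Very mild is taken as below the threshold.
- Levels: Appendix E. The frequency cut falls between one day and 2-3 days; the severity cut falls between mild and moderate.
- Baseline: a troublesome item, in line with inclusion criterion 3.

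**Cells**
- Baseline: 3 frequencies (2-3 days, 4-6 days, daily) × 4 severities (mild to severe) = 12.
- Follow-up: 1 (not present) + 5 frequencies × 5 severities = 26.
- Transitions: 12 × 26 = 312.

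**Changes that meet only the severity limb.** The baseline is moderate or worse (3 × 3 = 9 cells). Follow-up is very mild or mild, still on two or more days (2 × 3 = 6 cells). 9 × 6 = 54.
- Frequency worse: 3 rising frequency pairs × 3 baseline severities × 2 follow-up severities = 18.
- Still troublesome (follow-up mild): 9 × 3 = 27.
- Both: 3 × 3 × 1 = 9.

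**Changes that meet both limbs.** 9 baseline cells × (1 + 2 × 2 = 5 follow-up cells) = 45. Neither dimension can be worse.

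**Changes that meet only the frequency limb.** All that meet the frequency limb: 12 × (1 + 2 × 5 = 11) = 132. Less those meeting both limbs: 132 − 45 = 87.
- Severity worse: from mild 3 higher levels, from moderate 2, from moderately severe 1, so 6 × 3 baseline frequencies × 2 follow-up frequencies = 36.
- Still troublesome: 0, because frequency is one day or less.

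| Limb met | Transitions | Other dimension worse | Still troublesome | Both |
|---|---|---|---|---|
| Severity only | 54 | 18 | 27 | 9 |
| Frequency only | 87 | 36 | 0 | 0 |
| Both limbs | 45 | 0 | 0 | 0 |
| Total | 186 | 54 | 27 | 9 |

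The synopsis and Section 11.1 definitions of troublesome sort every RDQ cell the same way, since the form has no level between one day and 2-3 days. The result therefore does not depend on which is used.

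**With a no-worsening condition.** Responder transitions fall to 186 − 54 = 132, of which 27 − 9 = 18 are improved but still troublesome.

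**Free of troublesome symptoms but not a responder.** There are 26 − 12 = 14 non-troublesome follow-up cells, so 12 × 14 = 168 transitions end free. Under the current rule 186 − 27 = 159 of them are responders, leaving 9. With the condition 132 − 18 = 114 are responders, leaving 54.

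**Per patient.** With 50 evaluable patients, each one reclassified moves the rate by 1/50 = 2 percentage points. It moves more if fewer have data, since Section 10.1 (Analysis Populations and Missing Data Handling) analyses available data without imputation.

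**The case against.** The strongest reply is that the two sections measure different things. Section 8.1 measures improvement from baseline; Section 11.1 and Table 5 measure a status. A patient can improve and remain troublesome, and a plan may report both. This stands. A reader might infer that the responder rate contradicts the secondary endpoint, or overstates benefit against the protocol's own definition. The documents do not support that: they never say the two must agree, and the protocol's own definition of a clinically significant RDQ result is the Section 8.1 rule itself. Moderate daily symptoms becoming mild daily symptoms are a genuine partial improvement, even though the patient is still troublesome.

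Nor does every worsened responder conflict with the secondary endpoint. Severe symptoms on one day a week are not troublesome under Section 11.1 or the synopsis, so that patient succeeds on both measures. The objection to counting that patient is the rise in severity, not a clash between endpoints.

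It is also true that nothing formal depends on the rule, and that Section 10.2.2 summarises the RDQ as a continuous score and as change from baseline at 6 months. Those summaries give a wider picture but do not show which responders worsened on one dimension.

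None of this answers the missing no-worsening condition. A difference in purpose explains why an improved patient may still be troublesome; it does not explain why a patient whose severity or frequency has risen should be called improved.

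**Conclusion.** The point holds as a minor one. The rule allows a worsened dimension to be counted as clinically significant improvement in 54 of 186 qualifying single-item transitions: 36 through the frequency limb with severity worse, and 18 through the severity limb with frequency worse. These counts give each logical case equal weight and say nothing about how often patients would fall into them. The documents give no RDQ distribution, so the effect on the reported rate cannot be computed beyond the 2 points per patient at 50 evaluable.

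The counts assume a troublesome baseline item and a rule applied to one item. Section 8.1 does not say whether the rule works per item, per heartburn or regurgitation domain, or on the worst item; accepting a response on any one of several items would only add such cases. The two worked examples need none of the counting. The primary pH test, the sample size and the Table 5 success criteria are unaffected.

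**What to change.** Keep the either-limb rule as the measure of improvement and add one condition in Section 8.1: neither RDQ frequency nor RDQ severity may be at a higher level at 6 months than at baseline. State in the same place the unit to which the rule and the condition apply (item, domain or worst item).

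In Section 10.2.2, add a two-by-two table of RDQ response against Section 11.1 troublesome status at 6 months, so that patients who improved but are still troublesome can be seen.

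Do not require responders to be free of troublesome symptoms. That is already the secondary endpoint, and requiring it would make the responder rate nearly a copy of it and remove the categorical measure of partial RDQ improvement. Changing the connector so that both limbs are needed is no better: it leaves only the 45 both-limb transitions, and a patient with mild baseline severity could never respond.

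The cost is wording, settled before the 6-month data are analysed, using data already collected. The descriptive responder rate will be slightly lower, and some patients free of troublesome symptoms will not be RDQ responders, for example the one with severe symptoms on one day. The cross-tabulation shows those patients as well.
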